5.3.1.5. Dose Modification for Hepatic Impaired Subjects

Ibrutinib is metabolized in the liver and therefore subjects with clinically significant chronic hepatic impairment at the time of screening (Child- Pugh class B or C) are excluded from study participation. For subjects with existing chronic mild hepatic impairment (Child-Pugh class A) at enrollment, the starting dose has to be adjusted to a level of 280 mg daily (two capsules). For subjects who develop mild liver impairment while on study (Child-Pugh class A), the recommended dose reduction for ibrutinib is to a level of 280 mg daily (two capsules) unless lower doses had already been implemented. For subjects who develop moderate liver impairment while on study (Child-Pugh class B), the recommended dose reduction is to a level of 140 mg daily (one capsule). Subjects who develop severe hepatic impairment (Child-Pugh class C) must hold study drug until resolved to moderate impairment (Child-Pugh class B) or better. Monitor subjects for signs of toxicity and follow dose modification guidance as needed (Refer to Appendix 10 and Section 5.3.1.4).

5.3.2. Nivolumab

5.3.2.1. Formulation/Packaging/Storage

Nivolumab (also referred to as BMS-936558 or MDX-1106) 40 and/or 100 mg vials (10 mg/mL) will be supplied using commercial supply. Nivolumab is a programmed death receptor-1 (PD-1) blocking antibody. Nivolumab vials must be stored in the refrigerator at 2-8°C, protected from light and freezing. If stored in a glass front refrigerator, vials should be stored in the carton. The product does not contain a preservative, and as such after preparation, nivolumab infusions should be stored at room temperature for no more than 4 hours from time of preparation. This includes room temperature storage of infusion in IV container and time for administration of infusion. Alternatively, nivolumab infusion can be stored under refrigeration at 2 to 8 degrees C (36-46°F) for no more than 24 hours from the time of infusion preparation. The infusion should not be frozen.

Recommended safety measures for preparation and handling of nivolumab include laboratory coats and gloves. For complete details on drug preparation, administration, storage conditions, clinical pharmacology, pharmacokinetics, and known precautions and adverse reactions please refer to the Nivolumab package insert.

5.3.2.2. Dose and Administration

The drug product solution should be visually inspected for particulate matter and discoloration prior to administration. Nivolumab is a clear to opalescent, colorless to pale-yellow solution. Discard the vial if the solution is cloud, is discolored, or contains extraneous particulate matter other than a few translucent-to-white, proteinaceous particles. Do not shake the vial.

The required volume of nivolumab should be withdrawn and transferred into an intravenous container. Nivolumab should be then be diluted with either 0.9% sodium chloride injection, USP or 5% dextrose injection, USP, to prepare an infusion with a final concentration ranging from 1 mg/mL to 10 mg/mL. Diluted solution should be mixed by gentle inversion, but should not be shaken. Partially used or empty vials of nivolumab should be discarded.

Patients should be administered nivolumab 240 mg as an in intravenous infusion over 60 minutes every 2 weeks. For the first infusion, the patient's vital signs (heart rate, respiratory rate, blood pressures, and temperature) should be determined within 60 minutes before, during (every 15 [\pm 5] minutes), and 30 (\pm 10) minutes after the infusion. For subsequent infusions, vital signs will be collected within 60 minutes before infusion. Patients will be informed about the possibility of delayed post-infusion symptoms and instructed to contact their study physician if they develop acute symptoms.

Administer the infusion over 60 minutes through an intravenous line containing a sterile, nonpyrogenic, low protein binding in-line filter (pore size of 0.2 micrometer to 1.2 micrometer).

Do not coadminister other drugs through the same intravenous line.

Flush the intravenous line at end of infusion.

5.3.3. Management of Nivolumab-Specific Adverse Events

Toxicities associated or possibly associated with nivolumab treatment should be managed according to standard medical practice. Additional tests, such as autoimmune serology or biopsies, may be used to determine a possible immunogenic etiology.

Although most immune-related adverse events observed with immunomodulatory agents have been mild and self-limiting, such events should be recognized early and treated promptly to avoid potential major complications. Discontinuation of nivolumab may not have an immediate therapeutic effect and in severe cases, immune-related toxicities may require acute management with topical corticosteroids, systemic corticosteroids, mycophenolate, or TNF- α inhibitors.

The primary approach to Grade 1-2 immune-related adverse events is supportive and symptomatic care with continued treatment with nivolumab; for higher grade immune-related adverse events, nivolumab should be held and oral/parental steroids administered. Recurrent Grade 2 immune-related adverse events may also mandate holding nivolumab or the use of steroids. Consideration for benefit/risk balance should be made by the investigator, with consideration of the totality of information as it pertains to the nature of the toxicity and the degree of clinical benefit a given patient may be experiencing prior to further administration of nivolumab. Nivolumab should be permanently discontinued in patients with life-threatening irAEs.

See Prescribing Information for full details.

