5.3.4. Guidelines for Dosage Modification and Treatment Interruption or Discontinuation

Nivolumab treatment will be given for up to one year.

Patients may temporarily suspend study treatment for up to 42 days from the last dose if they experience toxicity that is considered related to the study drug and requires a dose to be held. If nivolumab is held because of adverse events for >42 days beyond the last dose, then the patient will be discontinued from nivolumab.

If a patient must be tapered off steroids used to treat adverse events, nivolumab may be held for additional time beyond 42 days from the last dose until steroids are discontinued or reduced to prednisone dose (or dose equivalent) ≤ 10 mg/day. The acceptable length of interruption will depend on an agreement between the investigator and the Principal Investigator.

Dose interruptions for reason(s) other than toxicity, such as surgical procedures, may be allowed with Principal Investigator approval. The acceptable length of interruption will depend on agreement between the investigator and the Principal Investigator.

Any toxicities associated or possibly associated with nivolumab treatment should be managed according to standard medical practice. Additional tests, such as autoimmune serology or biopsies, may be used to determine a possible immunogenic etiology.

Patients should be assessed clinically (including review of laboratory values) for toxicity prior to, during, and after each infusion. If unmanageable toxicity due to nivolumab occurs at any time during the study, treatment with nivolumab should be discontinued.

Management of potential immune related AEs are described in the following sections.

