5.3.4.2. Gastrointestinal Toxicity

Immune-mediated colitis has been associated with the administration of nivolumab. Diarrhea or colitis was reported in 21% of patients in two trials of nivolumab. Immune-mediated colitis occurred in 2.2% of patients in one trial- of these one patient had Grade 2 colitis, and five had Grade 3 colitis. In the other trial, Grade 3 immune-mediated colitis occurred in 0.9% of patients.

Patients should be advised to inform the investigator if any diarrhea occurs, even if it is mild. Range for time to onset of symptoms of colitis has been 1-6 months.

If the event is of significant duration or magnitude or is associated with signs of systemic inflammation or acute phase reactants (e.g. increased CRP or platelet count or bandemia), it is recommended that sigmoidoscopy (or colonoscopy, if appropriate) with colonic biopsy with three to five specimens for standard paraffin block be performed.

Treatment may be restarted following the resolution of colitis. In addition, if the patient is being managed with corticosteroids, treatment should not be restarted until the steroids have been tapered down to a prednisone dose \leq 10 mg/day. Patients who resume treatment should be monitored closely for signs of renewed diarrhea.

Table 2 provides a summary of dose modification guidelines for gastrointestinal toxicities.

Table 2 Dose Modification Guidelines for Gastrointestinal Toxicity

Symptoms	Management	Follow-up
Grade 1 diarrhea: <4 stools per day over baseline Grade 1 colitis: asymptomatic colitis	Continue nivolumab Administer symptomatic treatment	
 - Close monitoring for worsening symptoms - Educate patients to report worsening immediately
Grade 2 diarrhea: 4-6 stools per day over baseline 
 - IV fluids indicated <24 hrs - Not interfering with ADL Grade 2 Colitis: abdominal pain, blood in stool	Withhold nivolumab Administer symptomatic treatment If symptoms persist >5 days or recur: 0.5 to 1 mg/kg/day prednisone equivalents	
If improved:
 
 - resume nivolumab - if steroids have been administered, taper steroids over at least 1 month before resuming nivolumab 
If symptoms worsen or persist >3-5 days with oral steroids:
 
 - treat as Grade 3 or 4

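### Section 5.3.3 and the organ tables differ on nivolumab at Grade 2 and Grade 3, and no sentence expressly gives the tables precedence

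*Combined protocol and SAP*

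**What the plan says.** Section 5.3.3 gives general guidance by grade. At the lower grades, "The primary approach to Grade 1-2 immune-related adverse events is supportive and symptomatic care with continued treatment with nivolumab". Above that, nivolumab is held and steroids are given. One sentence qualifies the lower-grade rule: "Recurrent Grade 2 immune-related adverse events may also mandate holding nivolumab or the use of steroids". Two more bear on it: "Consideration for benefit/risk balance should be made by the investigator", and "Nivolumab should be permanently discontinued in patients with life-threatening irAEs". The section closes by referring to the prescribing information. It does not mention the tables.

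Section 5.3.4 follows directly and says: "Management of potential immune related AEs are described in the following sections". The organ sections then give Tables 2 (gastrointestinal), 3 (hepatic), 4 (renal), 5 (endocrine) and 6 (pulmonary). Sections 5.3.4.3, 5.3.4.4 and 5.3.4.6 direct that hepatic, renal and pulmonary events be managed by their tables. The gastrointestinal section is more descriptive: "Table 2 provides a summary of dose modification guidelines for gastrointestinal toxicities".

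The Grade 2 row of Table 2 says "Withhold nivolumab". The Grade 2 rows of Tables 3, 4 and 6 give the same instruction. None of the four makes the hold depend on recurrence.

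**The concern.** For a first Grade 2 event in four organ systems, the protocol gives two different instructions. Section 5.3.3 read literally continues nivolumab with supportive care; the organ table stops dosing until recovery and, outside the gastrointestinal tract, starts prednisone. At Grade 3, Section 5.3.3 holds nivolumab, while Tables 3 and 6 end it for good.

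The safety direction is clear. Followed literally, the general rule would keep a patient with a first Grade 2 pneumonitis on nivolumab without steroids, and Section 5.3.4.6 reports fatal immune-mediated pneumonitis in 5 of 691 patients. This is a new combination at two sites, which could read the text differently.

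There is also a smaller consequence for the data. Whether continuing nivolumab at a first Grade 2 event is a protocol deviation, reportable within 2 days (Section 12.7) and possibly relevant to the per-protocol population (Section 10.4.2), depends on which text governs.

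**Working it through.** **Step 1. The instructions side by side.**

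| Event | Section 5.3.3 | Organ table |
|---|---|---|
| First Grade 2, gastrointestinal | Continue, supportive care | Table 2: withhold; steroids only if symptoms last more than 5 days or recur |
| First Grade 2, hepatic | Continue, supportive care | Table 3: withhold; prednisone equivalent 1–2 mg/kg/day |
| First Grade 2, renal | Continue, supportive care | Table 4: withhold; prednisone equivalent 0.5–1 mg/kg/day |
| First Grade 2, pulmonary | Continue, supportive care | Table 6: withhold; prednisone or equivalent 1 mg/kg/day |
| Grade 3, hepatic or pulmonary | Hold, steroids | Tables 3 and 6: discontinue permanently, steroids |

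All four tables that are organized by grade differ from the general rule at Grade 2. Table 5 is organized by symptoms and is left out of the comparison.

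**Step 2. How many patients could meet both instructions at Grade 2.** The plan gives no figure for this. Inputs are the immune-mediated counts in Sections 5.3.4.2, 5.3.4.4 and 5.3.4.6, and N = 30 (Section 10.3).

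Formulas: expected patients = 30 × p; chance of at least one = 1 − (1 − p)^30.

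*Trial with 268 patients.*
- Colitis: "of these one patient had Grade 2 colitis, and five had Grade 3 colitis". That makes 6 cases; 6/268 = 2.24% matches the quoted 2.2%, so I take this to be the 268-patient trial. Grade 2: 1/268 × 30 = 0.11.
- Pneumonitis: 6 cases, one of them Grade 3. The Grade 2 count is missing from the text, so I take 6 − 1 = 5. 5/268 × 30 = 0.56.
- Renal: 2 cases reported as Grade 2 or 3 together, so 0 to 2 at Grade 2. 0 to 2/268 × 30 = 0 to 0.22.
- Sum: 6 to 8 of 268 (2.24% to 2.99%). Expected 0.67 to 0.90. Chance of at least one: 1 − (1 − 6/268)^30 = 49%, to 1 − (1 − 8/268)^30 = 60%.

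*Trial with 117 patients.*
- Renal: 1/117 × 30 = 0.26.
- Pneumonitis: 2/117 × 30 = 0.51.
- Grade 2 colitis taken as 0, because only Grade 3 is reported.
- Sum: 3 of 117 (2.56%). Expected 0.77. Chance of at least one: 1 − (1 − 3/117)^30 = 54%.

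Not counted: hepatitis (no rate given); diarrhea or colitis of any cause (21%) and raised creatinine (13% and 22%), because these are not split by grade or cause.

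**Step 3. Grade 3.** This is outside the count above. For pneumonitis alone the same arithmetic gives 1/268 × 30 = 0.11 and 5/117 × 30 = 1.28 patients. Grade 3 hepatitis again has no rate.

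**The case against.** The best defense is that Section 5.3.3 is an overview and the tables are the dosing instructions. It speaks of a primary approach, leaves a benefit/risk judgment to the investigator before further dosing, and forbids no one from holding at a first Grade 2 event. It is also needed for immune-related events that have no table, where nothing conflicts with it. Section 5.3.4 sends the reader onward, and three organ sections direct management by table. Even for gastrointestinal events, Table 2 is titled as dose modification guidelines. General guidance followed by organ-specific rules is ordinary protocol structure.

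Most of that stands. A reader might infer that the protocol leaves investigators with nothing to say which instruction to follow. The documents do not support this: the pointers above make the table the operative instruction for hepatic, renal and pulmonary events, and most readers would use Table 2 as well. What is absent is an express precedence clause.

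What the defense does not remove is the difference in wording. None of the qualifiers in Section 5.3.3 calls for a hold at a first Grade 2 event; by naming recurrent Grade 2 events for a possible hold, the section leaves first events under continuation. Nor does it refer the reader to the tables.

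**Conclusion.** The inconsistency is real and should be corrected, because the general rule as written is wrong for a first Grade 2 event in four organ systems and is weaker than Tables 3 and 6 at Grade 3. The practical effect is small. Under one of 30 patients (0.67 to 0.90) is expected to have a Grade 2 event to which both instructions apply.

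A reader might take the 49% to 60% as a chance of a dosing error. It is not: it is the chance that at least one such event occurs, and most investigators would then reach the table.

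The figures assume that the cited nivolumab rates carry over to this trial, that the trial and count identifications in the working are right, and that no patient has two of these events. Rates with ibrutinib added are unknown, and hepatitis could raise the count. The point does not touch the primary endpoint, alpha, power or sample size.

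**What to change.** Add to Section 5.3.3:

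> Where Tables 2–6 apply, they take precedence over the general guidance in this section at every grade, including withholding nivolumab at a first Grade 2 gastrointestinal, hepatic, renal or pulmonary event and permanent discontinuation at Grade 3 where the table requires it. The general guidance applies to immune-related events not covered by a table. Permanent discontinuation for life-threatening irAEs applies in all cases.

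Precedence should cover every grade: a clause limited to the Grade 1–2 rule would leave the Grade 3 difference in Tables 3 and 6 unranked. The last sentence is needed because Table 5 says only to withhold nivolumab for suspected adrenal crisis, and giving Table 5 precedence without it could be read as overriding the discontinuation rule.

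The cost is a few sentences, with no change to design, sample size or data collection. Under Section 12.9 an amendment needs approval from the ibrutinib supplier and then the IRB, so it is best bundled with another amendment.

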5.3.4. Guidelines for Dosage Modification and Treatment Interruption or Discontinuation

Nivolumab treatment will be given for up to one year.

Patients may temporarily suspend study treatment for up to 42 days from the last dose if they experience toxicity that is considered related to the study drug and requires a dose to be held. If nivolumab is held because of adverse events for >42 days beyond the last dose, then the patient will be discontinued from nivolumab.

If a patient must be tapered off steroids used to treat adverse events, nivolumab may be held for additional time beyond 42 days from the last dose until steroids are discontinued or reduced to prednisone dose (or dose equivalent) ≤ 10 mg/day. The acceptable length of interruption will depend on an agreement between the investigator and the Principal Investigator.

Dose interruptions for reason(s) other than toxicity, such as surgical procedures, may be allowed with Principal Investigator approval. The acceptable length of interruption will depend on agreement between the investigator and the Principal Investigator.

Any toxicities associated or possibly associated with nivolumab treatment should be managed according to standard medical practice. Additional tests, such as autoimmune serology or biopsies, may be used to determine a possible immunogenic etiology.

Patients should be assessed clinically (including review of laboratory values) for toxicity prior to, during, and after each infusion. If unmanageable toxicity due to nivolumab occurs at any time during the study, treatment with nivolumab should be discontinued.

Management of potential immune related AEs are described in the following sections.

5.3.4.1. Management of infusion-related reaction

No premedication will be allowed for the first dose of nivolumab. Premedication may be administered for 2 doses or greater at the discretion of the treating physician. Patients who experience infusion-associated symptoms may be treated symptomatically with antipyretics

(ibuprofen preferred), diphenhydramine, and/or cimetidine or another H2 receptor antagonist, as per standard practice.

The management of infusion-related reactions will be according to severity as per institutional guidelines.

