1.5.1. Risks

1.5.2. Bleeding-related events

There have been reports of hemorrhagic events in subjects treated with ibrutinib both with and without thrombocytopenia. These include primarily minor hemorrhagic events such as contusion, epistaxis, and petechiae; and some major hemorrhagic events including gastrointestinal bleeding, intracranial hemorrhage and hematuria. Use of ibrutinib in subjects requiring other anticoagulants or medications that inhibit platelet function may increase the risk of bleeding. Subjects with congenital bleeding diathesis have not been studied.

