3.2.1. Study Population And Treatment

The study will enroll adult subjects with pathologically determined renal cell cancer. This study will be conducted at the University of California Davis Comprehensive Cancer Center and at another site that is yet to be determined. There will be a total of 2 US sites.

Ibrutinib in combination with nivolumab will be investigated. The assigned treatment (Ibrutinib in combination with nivolumab) will continue in subjects for a maximum of 1 year or until progression, unacceptable or intolerable toxicity, physician choice (if in best interest of patient), or patient withdrawal for any reason. In the event that the patient is unable (due to toxicity or tolerability issues) or unwilling to receive both agents concurrently after the first two cycles, then single agent nivolumab can be administered at the investigator's discretion to complete one year of therapy. Treatment with ibrutinib will continue until either disease progression OR physician/patient choice OR unacceptable or intolerable toxicities.

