13. Currently active, clinically significant cardiovascular disease, such as uncontrolled arrhythmia or Class 3 or 4 congestive heart failure as defined by the New York Heart Association Functional Classification; or a history of myocardial infarction, unstable angina, or acute coronary syndrome within 6 months prior to enrollment.
14. Unable to swallow capsules or malabsorption syndrome, disease significantly affecting gastrointestinal function, or resection of the stomach or small bowel, symptomatic

inflammatory bowel disease or ulcerative colitis, or partial or complete bowel obstruction.

15. Lactating or pregnant.
16. Unwilling or unable to participate in all required study evaluations and procedures.
17. Unable to understand the purpose and risks of the study and to provide a signed and dated informed consent form (ICF) and authorization to use protected health information (in accordance with national and local subject privacy regulations).
18. Concomitant use of warfarin or other Vitamin K antagonists. Note: Subjects receiving antiplatelet agents in conjunction with ibrutinib should be observed closely for any signs of bleeding or bruising, and ibrutinib should be withheld in the event of any bleeding events. Supplements such as fish oil and vitamin E preparations should be avoided.
19. Requires treatment with a strong cytochrome P450 (CYP) 3A4/5 inhibitor. (see Appendix 3)
20. QT prolongation and/or familiar history of QT prolongation and uncontrolled cardiac arrhythmias that in the opinion of the investigator would interfere with the patient's safety or compliance on trial.
21. Currently active, clinically significant hepatic impairment Child-Pugh class B or C according to the Child Pugh classification (Appendix 10).

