5.2.1. Route and schedule

Repeat every 28 days

Dose Level	Nivolumab dose	Ibrutinib dose (days 1-28)*
Level 0	240 mg IV q2 weeks	560mg PO
Level -1	240 mg IV q2 weeks	420mg PO

*should be taken at the same time every day

Dose limiting toxicity (DLT) must be treatment-related (possibly, probably, or definitely). To be evaluable for DLT, the subject must have had one dose of Nivolumab and at least 3 weeks of Ibrutinib.

Dose limiting toxicity (DLT) is defined as:

- 1) Grade 4 absolute neutrophil count with fever (>101.4 F) or documented infection;
- 2) Grade 4 thrombocytopenia or Grade 3 thrombocytopenia with bleeding;
- 3) Any grade 3 or greater non-hematologic toxicity excluding alopecia.

DLT will be assessed after 1 cycle (4 weeks).

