5.3.1.4. Dose Modification for Adverse Reactions

The dose of study drug should be modified according to the dose modification guidelines in Table 1 if any of the following toxicities occur:

- Grade 4 ANC (<500/ μ L) for more than 7 days or fibroneutropenia.
- Grade 3 thrombocytopenia (<50,000/ μ L) in the presence of clinically significant bleeding events.
- Grade 4 thrombocytopenia (<25,000/ μ L).
- Grade 3 or 4 nausea, vomiting, or diarrhea if persistent, despite optimal anti-emetic and/or anti-diarrheal therapy.
- Any other Grade 4 or unmanageable Grade 3 toxicity.

For Grade 3 or 4 atrial fibrillation or persistent atrial fibrillation of any grade, consider the risks and benefits of ibrutinib treatment. If clinically indicated, the use of anticoagulants or antiplatelet agents may be considered for the thromboprophylaxis of atrial fibrillation (Section 6.2.4).

Note: After a dose reduction, dose escalation of ibrutinib to a previous higher dose is NOT allowed.

Table 1. Ibrutinib Dose Modifications

Occurrence	Action to be Taken
First	Withhold study drug until recovery to Grade ≤ 1 or baseline; may restart at original dose level
Second	Withhold study drug until recovery to Grade ≤ 1 or baseline; may restart at 1 dose level lower (ie, 280 mg/day for 420 mg/day dose; 420 mg/day for 560 mg /day dose)
Third	Withhold study drug until recovery to Grade ≤ 1 or baseline; may restart at 1 dose level lower (ie, 140 mg/day for 420 mg/day dose; 280 mg/day for 560 mg /day dose)
Fourth	Discontinue study drug

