6.2.4. Antiplatelet Agents and Anticoagulants

Warfarin or vitamin K antagonists should not be administered concomitantly with ibrutinib. In an in vitro platelet function study, inhibitory effects of ibrutinib on collagen-induced platelet aggregation were observed. Supplements such as fish oil and vitamin E preparations should be avoided. Use ibrutinib with caution in subjects requiring other anticoagulants or medications that inhibit platelet function. Bleeding events of any grade, including bruising and petechiae, occurred in subjects treated with ibrutinib. Subjects with congenital bleeding diathesis have not been studied. For guidance on ibrutinib and the use of anticoagulants during procedures/surgeries see Section 6.4.

Subjects requiring the initiation of therapeutic anticoagulation therapy (eg, atrial fibrillation), consider the risks and benefits of continuing ibrutinib treatment. If therapeutic anticoagulation is clinically indicated, treatment with ibrutinib should be held and not be restarted until the subject is clinically stable and has no signs of bleeding. Subjects should be observed closely for signs and symptoms of bleeding. No dose reduction is required when study drug is restarted.

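### Section 5.3.4.1 makes ibuprofen the preferred antipyretic for infusion symptoms in patients scheduled to take ibrutinib daily, which sits awkwardly with the platelet-function caution in 6.2.4; deleting the preference is a cheap, minor safety improvement

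*Combined protocol and SAP*

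**What the plan says.** Section 5.3.4.1 allows symptomatic treatment of infusion-associated symptoms and lists the options. One antipyretic is named, and it is ranked first: "ibuprofen preferred), diphenhydramine, and/or cimetidine or another H2 receptor antagonist, as per standard practice". The section gives no reason for the ranking and makes no exception for patients on ibrutinib. It then leaves infusion reactions to institutional guidelines according to severity. Premedication is not allowed at the first infusion and is discretionary after that.

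Four other places deal with drugs that affect platelets:

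- Section 6.2.4 reports an in vitro effect of ibrutinib on platelet aggregation and says: "Use ibrutinib with caution in subjects requiring other anticoagulants or medications that inhibit platelet function". It adds: "Supplements such as fish oil and vitamin E preparations should be avoided".
- Section 1.5.2 says: "Use of ibrutinib in subjects requiring other anticoagulants or medications that inhibit platelet function may increase the risk of bleeding".
- Section 4.2, exclusion 18, says: "Subjects receiving antiplatelet agents in conjunction with ibrutinib should be observed closely for any signs of bleeding or bruising". The same sentence goes on to require that ibrutinib be withheld if any bleeding occurs.
- Section 5.3.1.4 says that, if clinically indicated, "the use of anticoagulants or antiplatelet agents may be considered for the thromboprophylaxis of atrial fibrillation".

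Section 6.3, on prohibited medications, mentions neither ibuprofen nor its class.

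**The concern.** The choice of antipyretic for an infusion symptom is usually elective, since others could be used. The only steer the plan gives is toward a drug that, on general pharmacology, inhibits platelet function. The patients concerned are already taking a study drug for which the plan warns of bleeding, and the plan goes as far as discouraging fish oil and vitamin E. Section 4.1 also admits patients with platelet counts just above 50,000/mm³.

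What is at stake is avoidable exposure to a second platelet-inhibiting drug in patients who develop infusion symptoms. It is a patient-safety wording point and not a statistical one.

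**Working it through.** The plan gives no figure on this point to reproduce, so the check is a comparison of text plus one count from the schedule.

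**Step 1. Who is covered by 5.3.4.1?** Section 5.2.1 gives nivolumab every 2 weeks and heads the other column "Ibrutinib dose (days 1-28", so ibrutinib runs through the whole 28-day cycle. Section 3.2.1 provides for nivolumab alone only later, for a patient unable or "unwilling to receive both agents concurrently after the first two cycles, then single agent nivolumab can be administered". The scheduled overlap before that point is:

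- 2 cycles × 28 days = 56 days
- 56 days ÷ 14 days between infusions = 4 infusions

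All 4 are planned alongside daily ibrutinib, as are later infusions unless the patient moves to nivolumab alone. Two qualifications apply. Dose holds can change the count for an individual. Section 8.2.1 starts both drugs on cycle 1 day 1, so at the first infusion a patient has had at most one ibrutinib dose, with daily dosing to follow. The count describes scheduled infusions; it says nothing about how many produce symptoms, antipyretic doses or bleeds.

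**Step 2. Does 6.2.4 reach the choice of antipyretic?** As written, the caution governs the use of ibrutinib in subjects who require platelet-inhibiting medication. It is not addressed to choosing among as-needed medicines. It bears on 5.3.4.1 only with one added premise, that ibuprofen inhibits platelets. No section says so.

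**Step 3. Do the sections conflict?** Section 5.3.4.1 permits and prefers; 6.2.4 cautions; 6.3 does not prohibit. All three can be followed together: a clinician may give ibuprofen cautiously, or give something else. There is a tension but no contradiction.

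**Step 4. Does another section supply a reason for the ranking?** None does. Section 5.3.4.1 is the only place that names ibuprofen.

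**Step 5. Can the added risk be sized?** No. It would need the rate of infusion symptoms, the share treated with ibuprofen, and bleeding rates with and without it on this combination. The documents give none of these.

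**Step 6. Does anything statistical move?** No. The 15-of-25 rule in section 10.3 reproduces on its own inputs: exact one-sided alpha 0.0344 at 40% (stated 0.034) and power 0.902 at 70% (stated 90%). None of these inputs involves the antipyretic.

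**The case against.** The strongest case for leaving the text alone has five parts.

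1. **The pharmacology is not in the documents.** This is true. It is basic drug-class knowledge that the sponsor can check against the product label, but the clinical relevance of a brief course given with ibrutinib is not established here. That keeps the point small.

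2. **Clinicians already have discretion.** The wording is permissive and defers to standard practice and institutional guidelines, and the 6.2.4 caution applies without a cross-reference. This stands. Even so, a stated preference exists to guide choice, and nothing in the plan explains why it points to this drug.

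3. **Safeguards exist.** Exclusion 18 carries an action rule on bleeding, section 1.5.4 asks for monitoring for bruising and bleeding, section 5.3.4 requires toxicity assessment around each infusion, and section 11.4.6.1 captures major hemorrhage. These limit the harm. They act after exposure and do not guide the choice.

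4. **The plan accepts some antiplatelet use.** Section 5.3.1.4 allows it in atrial fibrillation, but only where there is a clinical indication. The choice among antipyretics is different in kind.

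5. **Alternatives have costs too.** The plan has its own liver precautions: entry with AST or ALT up to 3 × ULN (4.1), ibrutinib dose reduction in hepatic impairment (5.3.1.5), and review of concurrent medications when liver tests rise on nivolumab (5.3.4.3). The plan does not offer these as the reason for preferring ibuprofen, but they are a fair argument for naming no replacement.

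A reader might infer that the protocol recommends a drug it forbids, or that the preference measurably raises bleeding. The documents support neither: 6.2.4 is a caution, 6.3 contains no such ban, and no rate is available from which to measure an effect.

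**Conclusion.** The point holds as a minor, unreconciled tension. The plan states an unexplained preference for ibuprofen in a setting where most patients will be on ibrutinib, and elsewhere it urges caution when ibrutinib is used in patients who require platelet-inhibiting drugs.

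The conclusion rests on one assumption from outside the documents (ibuprofen inhibits platelet function) and one from the schedule (infusions mostly coincide with ibrutinib dosing). Its size cannot be stated as a risk; exposure would arise only in patients with infusion symptoms who are given the drug. It is an optional, low-cost improvement: the sponsor could make the change, and the trial does not depend on it.

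**What to change.** Delete the parenthesis (ibuprofen preferred) from section 5.3.4.1 outright, for all patients. The antipyretic is then chosen under standard practice and institutional guidelines, with 6.2.4 in mind, and ibuprofen stays permitted. A cross-reference to 6.2.4 alone would do less, because that caution already applies and the ranking would remain. Keeping the preference only for patients on nivolumab alone would need new conditional wording, since one parenthesis covers everyone; the gain does not justify it.

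The cost is two words, carried in the next amendment with the company review and IRB approval that section 12.9 requires. Sites lose a stated first choice, including for patients on nivolumab alone, and clinicians must weigh other antipyretics against the liver precautions in 4.1, 5.3.1.5 and 5.3.4.3. No patients, visits or data are added.
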